3.2.3 Relevant guidance documents

The following guidelines have also been considered in connection with the conduct of the RETENTION study:

(a) Health Technology Assessment agencies / EUnetHTA: This is not applicable for this study.

(b) Regulatory bodies (e.g., the European Medicines Agency, EMA1): No medicine development is included in the study.

(c) Clinical efficacy and safety guidelines for the evaluation of medicines in disease areas- e.g., diabetes (CPMP/EWP/1080/00 Rev. 1) or oncology (EMA/CHMP/EWP/205/95/Rev.4): Not applicable.

(d) General guidelines e.g., addressing clinical pharmacology and pharmacokinetics (e.g. bioanalytical methods validation EMEA/CHMP/EWP/192217/2009 Rev. 1 Corr. 2 or pharmacokinetics in paediatric population EMEA/CHMP/EWP/147013/2004): Not applicable.

(e) Methodological guidelines - e.g., statistical principles for clinical trials (CPMP/ICH/363/96) or clinical trials in small populations (CHMP/EWP/83561/2005): The clinical study will be conducted according to Good Clinical Practice (GCP), EU regulation (No 536/2014) and country specific legislations. Initially, the required RCT protocol files will be prepared and customised for each country. Informed Consent (ICF) will be

particularly emphasised to ensure compliance with the EU's General Data Protection Regulation (GDPR, 2016/679).

3.3 Regulatory status and activities

The randomised clinical study protocol will be designed and finalised according to current EU regulations, and ethics approvals will be obtained for all three clinical sites. The clinical protocol has been finalised at M13 (and is being delivered in the present document) instead of M8, approved by all sites, and in line with the Quality Assurance procedures of the RETENTION consortium. These procedures mostly entail peer reviewing amongst the members of the consortium and, if needed, from external actors. The actual protocol document will be formally submitted through Sygma EU platform. The list of deliverables for the clinical evaluation of RETENTION has been formulated taking into consideration the H2020 Guidelines on Clinical Trials. Compliance is mandatory for the call DTH-12-2020 under which RETENTION is submitted.

Additionally, all Principal Investigators from clinical centres will establish contact with relevant authorisation bodies to obtain approvals. The RETENTION study will be consistent with existing ethical and legal standards in relation to multi-centre trials. Processes within the project will ensure continual ethical scrutiny of activities throughout the lifetime of the project, as well as regulatory compliance.

3.3.1 Scientific advice / protocol assistance

Not applicable, no advice has been asked from a regulatory authority.

3.3.2 Qualification advice

This is a clinical study which will not involve any drug prescriptions other than those that would be required by established guidelines for the follow up and care of the recruited patients. The novelty in the study arises from the use of continuous patient monitoring outside hospitals collecting and analysing the aggregated data with state-of-the-art machine learning techniques. Their results provide the treating physician with better knowledge on the patient's daily status hence the decisions made on his/her behalf result in improved outcomes.

3.4 Subjects / Population(s)

3.4.1 Definition of sub-populations if subgroup analysis is intended

There will be two groups of patients. The first group will be subject to remote monitoring through the RETENTION platform but no additional intervention will be given other than the standard follow-up practice as it has been performed in the participating clinical centres during the last decade. The second group will be monitored and followed up on using the remote monitoring platform, and additional interventions will be provided as the system evolves with time based on the data analytics. All participants will take part in the clinical study after detailed explanation of the project's aims and their participation requirements. They will receive an information leaflet and will sign an informed consent form. They will be able to leave the clinical study at any point without any kind of explanation necessary. All participants will be assessed at baseline, and at months 4,8,12 and 18.

A total of 450 patients across the six hospitals will participate in the project. These patients will include:

- 200 patients with HF not enlisted for transplant at the time of their recruitment (approximately 44% of the total number of patients)
- 150 LVAD patients (approximately 34% of the total number of patients)

100 heart transplant recipients (approximately 22% of the total number of patients)

Of these patients 225 patients will be the test group, referred to as remote patient monitoring and interventions group (RPMI group), and 225 patients will be the control group, referred to as remote patient monitoring and usual care (RPMUC group). The control and the test group for each site will have equal numbers of recruits in each of the above three categories of patients. Of the recruited patients 30-35% will be women. This is because up until now, women have been underrepresented in most heart failure clinical trials, despite the fact that the disease prevalence remains generally the same between both sexes. The individual clinical units which will participate in the study are expected to recruit the numbers of patient shown in Table 1.

Table 1: Recruitment targets for individual clinical partners and countries							
Partner	Clinical Unit	No of Patients	Country				
OCSC	OCSC	100	Greece				
NKUA	NKUA	80	Greece				
UNIBO	UNIBO	100	Italy				
UKESSEN	UKESSEN	100	Germany				
SERMAS	Hospital Universitario Ramón y Cajal (SERMAS-HURC)	70	Spain				

4 5 Ta

3.4.2 Inclusion criteria

In order to be eligible for participation in the study, the subject must fulfil all of the required inclusion criteria. These are classified as general criteria that apply to all subjects and criteria that apply specifically and solely to heart failure, VAD and heart transplant patients, respectively.

General inclusion criteria (applying to all subjects):

- Age of 18-75 years
- Ability to understand and provide consent to participate in the study

Hospital UniversitarioPuerta de Hierro (SERMAS-HUPH)

- Have a cognitive assessment score of > 22 as assessed by the Montreal Cognitive Assessment (MoCA), i.e., adults without or with mild cognitive impairment at most
- Have a depression score as assessed by Personal Health Questionnaire-9 (PHQ-9) score < 10
- Provide written informed consent

Inclusion criteria for Heart Failure patients:

- Have a diagnosis of symptomatic heart failure, class II or III according to the New York Heart • Association (NYHA) Classification
- Have echocardiographically determined left ventricular ejection fraction (LVEF) ≤40%
- Have been hospitalised due to cardiovascular reasons or had urgent visit to the Emergency • Department due to decompensated HF that required administration of intravenous diuretics within the last 12 months before randomisation.

Currently hospitalised patients can be included provided they do not fulfil exclusion criterion #1that concerns current in-hospital administration of IV diuretics/vasoactive/inotropic drugs.

Inclusion criteria for patients with ventricular assist devices (VAD):

• Have left ventricular assist device (LVAD) implanted either as destination therapy or as bridge-totransplantation, within at least 90 days and no longer than 48 months before randomisation

Inclusion criteria for heart transplant recipients:

• Have been discharged following heart transplantation within at least 30 days and no longer than 36 months before study randomisation.

3.4.3 Exclusion criteria

The subject must be excluded from participating in the study if fulfils any of the following criteria:

- Is clinically unstable at the time of randomisation as defined by:
 - Administration of IV diuretics during the last 12 hours or IV vasodilators or inotropes during the last 48 hours before randomisation
- Has acute coronary syndrome within the last 30 days before randomisation
- Has acute inflammatory heart disease, e.g. acute myocarditis, within 90 days prior to randomisation
- Has a planned revascularisation, cardiac resynchronisation therapy (CRT) implantation or any valvular procedures within 3 months after randomisation
- Has known current alcohol or illicit drug abuse
- Has end-stage renal disease requiring haemodialysis
- Shows significant impairment or unwillingness to use the telemonitoring equipment (e.g., dementia, impaired self-determination, lacking ability to communicate)
- Has any severe non-cardiovascular disease limiting life expectancy to less than 1 year
- Is pregnant
- Participates currently in other telemonitoring programs/studies using smart devices

3.5 Statistical analysis plan and power calculation

The power analysis for the clinical study of RETENTION is based on a similar analysis performed for the TIM-HF-2 evaluating a telemonitoring intervention² with similar endpoints and considering similar inclusion criteria:

- Chronic heart failure New York Heart Association (NYHA) class II or III
- Echocardiographically determined left ventricular ejection fraction (LVEF) ≤45%
- Hospitalisation due to decompensated HF within the last 12months before randomisation
- Depression score PHQ-9<10

For the sample size calculation, TIM-HF-2 used data for specific subgroups from the TIM-HF trial for sample size calculations. For the patient subgroup that mirrored the population they did include in the TIM-HF-2 trial, 19 days were lost due to all-cause death or unplanned cardiovascular hospital admissions at 12 months

² Koehler F, Koehler K, Deckwart O et. al. Lancet. 2018 Sep 22;392(10152):1047-1057. doi: 10.1016/S0140-6736(18)31880-4. Epub 2018 Aug 25. PMID: 30153985.

in the usual care group, and 12 days were lost for patients in the remote patient management group, which corresponds to a 38% reduction. The estimated standard deviation (pooled) was 48 and based on that they calculated that 750 patients would be required in each group to detect this difference with a power of 80% and a two-sided α of 5%.

For RETENTION we expect a slightly higher decrease in the endpoint (40%). If we apply the same rate of losses TIM-HF trial for control group(19 days per year) to a follow up period of 18 months, we expect a mean of 29 (19+10) days lost due to all-cause death or unplanned cardiovascular hospital admissions in the usual care group and 17 days lost in the test group (-40% of 29). Under these assumptions, the number of patients for each group of the study should be 199 (398 in total). Hence, accounting for about 10% of attrition rate and loss to follow up, the recruitment target for the study has been set to 450 patients.

Group sample sizes of 199 and 199 achieve 80% power to reject the null hypothesis of equal means difference with a standard deviation for both groups of 48 and with a significance level (alpha) of 0,05 using a one-sided test.

Statistical analysis plan

- Demographic, clinical, and device data, and treatment results will be summarised using descriptive summary statistics. Data collected in the trial will be summarised overall and by treatment groups. Continuous variables will be presented with the numbers of observations, means, standard deviations, minimums, and maximums. For comparisons, the difference between the groups will be summarised with the difference of the two means together with 95% confidence intervals and tested using the two-sample t-test. These calculations will be done under the assumption that the data for the two groups are independent and approximately gaussian in distribution. If asymptotic assumptions fail, nonparametric summary statistics (medians, 25th and 75th percentiles) may be displayed. In addition, more appropriate non-parametric tests will be considered if the assumptions for the parametric tests are violated. For the comparison of two independent samples, if the data are not normally distributed, Mann-Whitney rank sum test will be performed instead of the parametric t-test,
- For categorical variables results will be summarised with subject counts, percentages. The differences between the two treatment groups will be summarised with the difference in percent and compared using the chi-square test or Fisher's exact test as appropriate.
- Survival analysis techniques will be used to analyse the time-to-event variables.

The primary analyses will compare the days lost due to unplanned cardiovascular hospitalisations or all-cause death and the survival free from death or unplanned hospitalisation/ambulatory administration of intravenous therapy between interventions group and usual care group by the means of the parametric t-test or non-parametric rank sum test as mentioned above.

To evaluate the additional measure of the primary outcome, the survival free from the combined endpoint, survival curves will be constructed using Kaplan-Meier estimates. Log-rank test results will also be computed for comparison of survival distributions between intervention and usual care groups.

Pre-specified subgroup analyses include:

- The three patient categories (HF, LVAD and HT)
- Males and Females
- Patients with a hospitalisation less than three months from the enrolment

• Patients older than 60 years

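### The 80% power uses a control rate and SD from a heart-failure trial, but 250 of the 450 patients (56%) have an LVAD or a transplant, and the protocol gives no basis for applying those values to them

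*Protocol*

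**What the plan says.** Section 3.5 bases the sample size on an earlier telemonitoring trial in heart failure "with similar endpoints and considering similar inclusion criteria". It lists four such criteria: NYHA class II or III, LVEF at or below 45%, hospitalisation for decompensated heart failure in the previous 12 months, and PHQ-9 below 10.

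The SD is the source's ("The estimated standard deviation (pooled) was 48"), carried over "with a standard deviation for both groups of 48". The source's control rate of 19 days per year is stretched to 18 months: "we expect a mean of 29 (19+10) days lost". The reduction of 40% is the protocol's own expectation, set slightly above the 38% reported for the source. The result is "Group sample sizes of 199 and 199 achieve 80% power", "with a significance level (alpha) of 0,05 using a one-sided test".

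Section 3.4.1 plans 200 heart-failure patients, "150 LVAD patients (approximately 34% of the total number of patients") and "100 heart transplant recipients (approximately 22% of the total number of patients"). Section 3.4.2 separates general criteria from criteria specific to each patient type. NYHA class, LVEF and prior admission stand only in the heart-failure list. LVAD and transplant patients enter on time since implant or discharge. PHQ-9 below 10 is a general criterion for everyone.

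Section 3.2.1 stratifies randomisation by centre and patient type. Section 3.5 names a two-sample t-test or rank-sum test for the primary comparison, with no stratification.

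**The concern.** The protocol treats the three patient types as distinct nearly everywhere: in eligibility, in randomisation, in the pre-specified subgroups, and in endpoints such as rejection and driveline infection. Only the power calculation treats all 450 as one heart-failure population. It offers no control mean, SD or effect for LVAD or transplant patients, and no reason for lending them the heart-failure values. If days lost, their spread, or the benefit of monitoring differ by type, the power of the pooled comparison is not the stated 80%.

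A smaller, related matter is that the named primary test ignores patient type although allocation is stratified on it.

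**Working it through.** **Share of the sample.** (150 + 100)/450 = 55.6%; heart failure is 200/450 = 44.4%.

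**Criteria side by side.**

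| Criterion listed for the source (3.5) | Heart-failure patients (3.4.2) | LVAD and transplant patients (3.4.2) |
|---|---|---|
| NYHA II or III | required | not required |
| LVEF ≤45% | required, at ≤40% | not required |
| Hospitalisation for decompensated HF within 12 months | cardiovascular hospitalisation, or urgent visit for decompensated HF needing IV diuretics, within 12 months | not required |
| PHQ-9 <10 | required | required |

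**The plan's own figure.** Inputs from section 3.5: difference 29 − 17 = 12 days, SD 48, 199 per arm, one-sided 5%.
- Sample size: 2 × (48/12)² × (1.645 + 0.842)² = 197.8 per arm by the normal approximation, 198.5 by the t-test, so 199.
- Standard error of the difference: 48 × √(2/199) = 4.81. Power: Φ(12/4.81 − 1.645) = Φ(0.849) = 80.2%; the t-test gives 80.1%.

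The arithmetic is sound. The question is where the inputs come from.

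**Power for the 200/150/100 mix.** The documents give no LVAD or transplant values, so the rows below are assumptions. All use 199 per arm, one-sided 5%, within-type SD 48, and a mix unchanged by attrition.

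Absolute effect: heart-failure patients gain 12 days and the others gain e days. Overall difference = 0.444 × 12 + 0.556 × e.

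| e (days) | Overall difference | Power | Needed per arm for 80% |
|---|---|---|---|
| 0 | 5.33 | 30% | 1002 |
| 6 | 8.67 | 56% | 380 |
| 9 | 10.33 | 69% | 267 |
| 12 | 12.00 | 80% | 198 |
| 18 | 15.33 | 94% | 122 |

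Relative effect: 40% reduction in everyone, heart-failure control mean 29, LVAD and transplant control mean m. Overall difference = 0.4 × (0.444 × 29 + 0.556 × m).

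| m (days) | Pooled control mean | Difference | Power |
|---|---|---|---|
| 15 | 21.2 | 8.49 | 54–55% |
| 20 | 24.0 | 9.60 | 63–64% |
| 29 | 29.0 | 11.60 | 78% |
| 40 | 35.1 | 14.04 | 90% |

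The m = 29 row gives 78% rather than 80% because 40% of 29 is 11.6, which the protocol rounds to 12.

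**What ignoring patient type costs.** Differences in mean between types enter the SD of an unstratified test.
- Control means 29/15/15: between-type variance is 0.444 × 0.556 × 14² = 48.4 in the control arm and 0.36 × 48.4 = 17.4 in the test arm, averaging 32.9. SD = √(2304 + 32.9) = 48.3. Power is 54.1% unstratified and 54.6% within type.
- Control means 29/60/15 (heart failure/LVAD/transplant), a deliberately wide spread: the pooled control mean is 36.2 and the difference 14.5. Between-type variances are 311.7 and 112.2, so SD = √(2304 + 212.0) = 50.2. Power is 89% unstratified and 91% within type.

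The gain is about 0.5 to 2 points.

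**The case against.** The strongest reply is that the 80% is correct for the inputs stated, and that the protocol presents it as holding under its assumptions. No figure in the documents shows that LVAD or transplant patients differ from heart-failure patients in mean, SD or effect, and other equally undocumented values raise power. All of this stands. What remains is that the only justification offered, similar inclusion criteria, does not cover 56% of the sample.

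Stronger readings are tempting but not supported:
- A reader might infer that LVAD and transplant patients meet none of the source criteria. PHQ-9 below 10 applies to them, and a criterion that is not required may still be met by individual patients.
- A reader might attribute the 40% effect to the heart-failure source. The source's figure was 38%; the 40% is the protocol's own expectation, though it too is given no LVAD or transplant basis.
- A reader might quote about 51% power, which is what roughly 90 heart-failure patients per arm would give. That is a subgroup figure. The primary test uses all patients.

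On the analysis, an unadjusted test after stratified randomisation is valid and if anything slightly conservative, patient type is already a pre-specified subgroup, and covariates are often left to the SAP. That makes this part an improvement rather than the correction of an error. But section 3.5 does name the primary test, so the protocol is not silent on the matter.

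**Conclusion.** The concern holds in limited form. The 80% is arithmetically right but conditional on LVAD and transplant patients sharing the heart-failure mean, SD and effect, a condition the protocol neither states nor supports. A reader might conclude that the trial is underpowered, or that the realistic range is mostly worse than 80%. The documents do not support that: the direction is unknown, and how many scenarios fall below 80% depends only on which are chosen. The scenarios tabulated run from 30% to 94%, all on assumed LVAD and transplant inputs with the protocol's SD of 48 and one-sided 5% level held fixed. Between-type spread is a minor matter, at about 0.5 to 2 points of power.

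**What to change.** 1. In section 3.5, confine the statement about similar inclusion criteria to the heart-failure category. Say that 80% holds only if the LVAD and transplant groups share the heart-failure mean, SD and effect. Give the assumed values for each type with their basis where one exists, and report power for the 200/150/100 mix over a range that extends both below and above 80%.
2. Replace the unstratified primary t-test or rank-sum test with a comparison of arms within patient type, for example a linear model with a term for type or a stratified rank test. The precision gain is small, but the analysis then matches the randomisation.

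The cost is protocol wording and one model term or stratification factor. No extra patients or data are needed. The single power figure becomes a conditional range.

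### The stated 40% reduction does not match the means used: 29 against 17 days is about 41–42%, and at a true 40% reduction 199 per group gives about 76–78% power, not 80%

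*Protocol*

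**What the plan says.** All the inputs stand in protocol section 3.5.

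- **Effect:** "we expect a slightly higher decrease in the endpoint (40"%).
- **Benchmark rate:** the control-group loss from the earlier telemonitoring trial is carried forward as "19 days per year) to a follow up period of 18 months".
- **Control mean:** "we expect a mean of 29 (19+10) days lost".
- **Test mean:** "17 days lost in the test group (-40% of 29").
- **Variability and test:** "with a standard deviation for both groups of 48" and a "significance level (alpha) of 0,05 using a one-sided test".
- **Result:** "the number of patients for each group of the study should be 199 (398 in total"), and "Group sample sizes of 199 and 199 achieve 80% power".

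The section then allows about 10% for attrition and sets the recruitment target at 450, which is 225 per group.

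**The concern.** The section names a relative reduction, converts it into two whole-day means, and bases the sample size on those means. The conversion does not preserve the named reduction. The control mean is rounded up and the test mean is rounded down, so both steps widen the difference between groups.

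Sample size varies with the inverse square of that difference, so a fraction of a day is visible in the result. A reader who takes the paragraph at its word will believe the trial has 80% power to detect a 40% reduction. It has 80% power to detect a somewhat larger one. At stake is the accuracy of the headline power statement, not the design.

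**Working it through.** **Inputs (all from section 3.5).** Benchmark 19 days per year; follow-up 18 months; reduction 40%; SD 48 in each group; one-sided alpha 0.05; target power 80%; 1:1 allocation; 450 recruited with about 10% lost.

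**Step 1: the means.**

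- Control over 18 months: 19 × 1.5 = 28.5. The plan adds 10 for the half year, where half of 19 is 9.5, and uses 29.
- Test group at 40% off the plan's own 29: 0.6 × 29 = 17.4. At 40% off 28.5: 0.6 × 28.5 = 17.1. The plan uses 17.
- Difference used: 29 − 17 = 12 days. Relative to the control mean this is 12/29 = 41.4%, or 12/28.5 = 42.1%.
- Difference at exactly 40%: 29 − 17.4 = 11.6 days, or 28.5 − 17.1 = 11.4 days.

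Of the 0.6-day gap between 11.4 and 12, rounding the control mean adds 0.2 days (40% of 0.5) and rounding 17.4 to 17 adds 0.4.

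**Step 2: reproduce the plan.** The normal approximation is n per group = 2 × (1.645 + 0.842)² × 48² / difference². With 12 days this gives 198; the two-sample t-test version gives 198.5, rounded up to 199. Power at 199 per group is 80.1% (t-test) or 80.2% (normal). The plan's figure is reproduced.

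**Step 3: the same calculation at 40%.** SD, test and alpha are held as stated; figures are from the t-test.

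| Means (days) | Difference | Reduction | n per group for 80% | Power at 199 | Power at 202 |
|---|---|---|---|---|---|
| 29 vs 17 (plan) | 12.0 | 41.4% of 29 | 199 | 80.1% | 80.6% |
| 29 vs 17.4 | 11.6 | 40% | 213 | 77.7% | 78.2% |
| 28.5 vs 17.1 | 11.4 | 40% | 220 | 76.4% | 77.0% |

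The 202 is what remains per group if 10% of 450 are lost: 450 × 0.9 = 405, or 202.5 per group. If all 225 per group were evaluable, power at 11.4 days would be about 81%.

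**Step 4: size against the attrition allowance.** The allowance is 450 − 398 = 52 patients. For 80% power at 40%, the evaluable total rises from 398 to 426 (28 more) or 440 (42 more).

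**Step 5: how exact the inputs are.** The benchmark means are themselves rounded: section 3.5 calls 19 against 12 days a 38% reduction, while 7/19 = 36.8%. If 19 stands for anything from 18.5 to 19.5 (an assumption about the rounding), a 40% reduction over 18 months is 0.4 × 1.5 × 18.5 = 11.1 days to 0.4 × 1.5 × 19.5 = 11.7 days. Power at 199 per group is then 74.5% to 78.3%. No value in that range reaches 12 days.

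**The case against.** The strongest reply is that nothing was miscalculated. The plan prints the means it uses, and 199 per group with 80% power is correct for 29 against 17. That stands. A reader might infer from the mismatch that the sample size does not follow from the plan's inputs; the text does not support that. It follows from the printed means. What does not match is the 40% attached to them.

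Second, the strict internal contradiction is only 17 against 17.4, because the plan openly states 29 as its control mean. On that reading the gap is 2.4 points at 199 per group (80.1% to 77.7%). This also stands, and is why the shortfall is given as a range; the lower figure requires setting aside the stated 29 in favour of 28.5.

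Third, each step is ordinary rounding to a whole day. Nothing in the section suggests the direction was chosen to favour the trial, and no such inference should be drawn. The two steps nevertheless add up in the same direction.

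Fourth, a reader might infer that the rounding consumes the whole attrition allowance. It does not: 28 to 42 extra patients is less than 52.

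Finally, the same paragraph rests on assumptions that could move power further. The SD of 48 comes from 12 months and is not rescaled for 18, and the test is one-sided. A two-sided 5% test at 12 days and SD 48 would give about 70% at 199 per group. That does not remove this point, which holds both fixed, but any restated power must be labelled as conditional on them.

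**Conclusion.** The point holds as a modest arithmetic inconsistency. The stated 40% reduction, 199 per group and 80% power cannot all be true together. Keeping 199 and 80%, the reduction is 12 days, or about 41–42%. Keeping 40% and 199, the power is about 78% if the control mean of 29 is retained and about 76% if the 18-month figure is carried unrounded. After the planned attrition these become about 78% and 77%.

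These figures rest on the plan's SD of 48, its one-sided 5% test and a two-sample t-test. They show a mislabelled effect size worth about 2 to 4 points of power. They do not show that the trial needs more patients or that its design is unsound.

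**What to change.** Amend the sample-size paragraph in section 3.5 in one of two ways.

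1. Keep 199 per group and 80% power, state that the trial is sized to detect a 12-day difference (29 against 17 days, about 41% of 29 or 42% of 28.5), and delete the 40% claim. This is the simpler choice, because it issues no new power figure.
2. Keep the 40% reduction, correct the means to 29 and 17.4 or to 28.5 and 17.1, and restate the power as about 76–78% at 199 per group (about 77–78% at about 202 after 10% attrition). Say that this is conditional on an SD of 48 and a one-sided 5% test.

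Either way the cost is one paragraph. Recruitment, design and analysis are unchanged. The only downside is a slightly less favourable statement: a larger assumed effect under the first option, or power 2 to 4 points lower under the second.

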3.2.2 Primary and secondary endpoints

The **primary study outcome** will be the days lost (%) due to unplanned cardiovascular hospitalisations or allcause death, comparing remote patient monitoring and interventions (RPMI) group with remote patient monitoring and usual care (RPMUC) group only during the individual follow-up time.

As additional measure of this primary outcome we will report the freedom from the combined occurrence of death or unplanned hospitalisation/ambulatory administration of intravenous (IV) diuretics, IV antibiotics, or intravenous (IV) steroids.

The secondary end-points include:

a. All-cause mortality during the individual follow-up time (to a maximum of 575 days, i.e., the 547 days of the patient monitoring period plus 28 days from the final study visit)

b. Cardiovascular mortality during the individual follow-up time (to a maximum of 575 days, i.e., the 574 days

¹ A delay of 5+ months was encountered in the completion of the present document D8.2, in relation to the study protocol and the evaluation framework. This delay inevitably affects the progress of the next project phases and will eventually result in a time shift for platform completion. At the time of submission of the present deliverable, the estimated minimum shift is ~3 months, therefore the onset of the trial study is shifted from the originally planned M19 to M22, and will end at M48 instead of 45, at the earliest. Accordingly, all trial internal phases are shifting as well, following the new estimated plan.

- of the patient monitoring period plus 28 days from the final study visit)
- c. Time to first unplanned HF hospitalisation
- d. Time to first unplanned cardiovascular hospitalisation
- e. Total unplanned HF hospitalisations (recurrent event analysis)
- f. Total unplanned cardiovascular hospitalisations (recurrent event analysis)
- g. Days (%) lost due to HF hospitalisations during the individual follow-up time.
- h. Number of smart device alarm notifications.

i. Change in the Kansas City Cardiomyopathy Questionnaire score between baseline (i.e., when a patient enters the study) and month 18.

j. Change in the levels of N-terminal pro-B-type natriuretic peptide (NT-proBNP) between baseline and month 18.

k. Change in the Depression Score Patient Health Questionnaire 9 (PHQ-9) score between baseline and month 18.

I. Change in the Heart Failure Caregiver Questionnaire (HF-CQ version 5.0) between baseline and month 18.

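### The 199 per arm and 80% power pair an 18-month difference in days lost with a 12-month standard deviation, and no reason is given

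*Protocol*

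**What the plan says.** The power calculation in Protocol Section 3.5 borrows from an earlier telemonitoring trial in heart failure. In that trial's usual care group, "19 days were lost due to all-cause death or unplanned cardiovascular hospital admissions at 12 months", while "12 days were lost for patients in the remote patient management group, which corresponds to a 38% reduction". On variability it says: "The estimated standard deviation (pooled) was 48 and based on that they calculated that 750 patients would be required in each group", for 80% power at a two-sided 5% level.

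For its own 18-month follow-up the Protocol applies the same yearly rate to the control group: "we expect a mean of 29 (19+10) days lost due to all-cause death or unplanned cardiovascular hospital admissions in the usual care group". With an assumed 40% reduction it expects 17 days in the test group, a difference of 12. It then states that 199 per group "achieve 80% power to reject the null hypothesis of equal means difference with a standard deviation for both groups of 48", "with a significance level (alpha) of 0,05 using a one-sided test". Allowing about 10% for attrition, the target becomes 450.

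Section 3.2.2 defines the primary outcome as "the days lost (%) due to unplanned cardiovascular hospitalisations or allcause death" over individual follow-up. Secondary endpoint a in that section gives the monitoring period as 547 days.

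**The concern.** The mean, and with it the difference to be detected, was multiplied by about 1.5 to move from 12 to 18 months. The SD was left at its 12-month value, and the Protocol gives no reason for treating the two differently.

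Days lost is a cumulative quantity. More follow-up means more admissions and more deaths, and a death can cost up to 547 days instead of 365. An SD that stays at 48 while the mean rises by half therefore needs an argument.

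The recruitment target and the 80% power claim both rest on this step. If the SD does grow, a true 40% reduction would be missed more often than the stated one time in five. A null result could then be read as stronger evidence against the intervention than it is.

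**Working it through.** **Inputs, all from Section 3.5 unless noted.** Control mean 19 days and SD 48 at 12 months; source difference 19 − 12 = 7; control mean 29 and test mean 17 at 18 months; 40% reduction; n = 199 per group; one-sided 5%; 547 days of monitoring (Section 3.2.2). The 18-month SD is not given, so the values below are assumptions.

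**Formulas.** Power ≈ Φ(d / (SD × √(2/n)) − 1.645). Sample size per group ≈ 2 × (1.645 + 0.842)² × (SD/d)². Powers below were checked with the noncentral t, which differs by at most a few tenths of a percentage point.

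**1. The Protocol's own figure.** d = 12, SD = 48, n = 199: 12 / (48 × √(2/199)) = 2.49; 2.49 − 1.645 = 0.85; power 80.2% (noncentral t 80.1%). The stated figure reproduces.

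**2. Which period the SD belongs to.** d = 7, SD = 48, two-sided 5%, 80% power gives about 740 per group, against the 750 reported for the source trial. So 48 goes with the 12-month difference of 7.

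**3. What the mixed time scales do to the effect size.** A 40% effect at 12 months is 0.40 × 19 = 7.6 days, and 7.6/48 = 0.158. The Protocol uses 12/48 = 0.25. With everything kept at 12 months (d = 7.6, SD = 48), power at 199 per arm is about 47%, and 494 per arm would be needed. This step assumes nothing about SD growth.

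**4. On the endpoint's percentage scale.** The control mean hardly moves: 19/365 = 5.2% and 29/547 = 5.3%. An unchanged SD of 48 days, however, means a fall from 48/365 = 13.2% to 48/547 = 8.8%. If the SD stays at 13.2%, the effect size is (12/547)/(48/365) = 0.167 and power is about 51%.

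**5. Letting the SD grow (assumed), d = 12, one-sided 5%.**

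| 18-month SD | Power, 199 per arm | Power, 225 per arm | n per arm for 80% | Detectable difference, 199 per arm |
|---|---|---|---|---|
| 48 (Protocol) | 80% | – | 199 | 12 days |
| 48 × √1.5 = 58.8 | 65% | 70% | 298 | about 15 days |
| 48 × 1.5 = 72 | 51% | 55% | 446 | about 18 days |

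The square-root row corresponds to independent contributions from successive periods. The proportional row corresponds to a constant SD on the percentage scale. The detectable difference is 2.487 × SD × √(2/199).

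**6. Rounding, a separate and minor matter.** 40% of 29 is 11.6 days, and 40% of the unrounded 28.5 (19 × 1.5) is 11.4. At SD 48 these alone lower power from 80% to 78% and 76%.

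**The case against.** The strongest reply is that the calculation is not wrong as arithmetic: 12 days, SD 48, 199 per group and a one-sided 5% test do give 80%. Every lower power at a 12-day difference needs an 18-month SD that the document does not contain. This stands. The fault is an unexplained mismatch between inputs, and the 51% to 65% is conditional on assumed growth.

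The SD for this population is also unknown. The 48 comes from a heart failure subgroup, whereas Section 3.4.1 plans 250 of 450 patients (56%) with an LVAD or a transplant. This stands too. It means that neither 58.8 nor 72 should be treated as the right value, and that square-root growth is not a guaranteed best case. It does not support keeping 48.

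Third, if all 225 per arm were evaluable, power would be higher. It would, at about 70% and 55%, still below 80%.

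Finally, the calculations are for a t-test, while Section 3.5 allows a rank sum test if the data are not normal. They therefore test the stated power claim and do not predict how the final analysis will perform.

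A reader might go further and infer that deaths push the SD well above 72, so that power falls below the range given here. The document does not support this. A death-driven SD cannot be paired with a 12-day difference, because days lost to death also raise the mean faster than follow-up time. In an illustrative model with assumed constant mortality, matched to mean 19 and SD 48 at 12 months, the 18-month mean is about 35 and the SD about 85. A 40% effect is then about 14 days, 14/85 = 0.165, and power is again about 50%.

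**Conclusion.** The concern holds as a mismatch of time scales. The 80% power at 199 per arm depends on an 18-month difference and a 12-month SD, and nothing else in the Protocol justifies or repairs this. There is almost no margin: power is already about 78% at an SD of 49.5.

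Under assumed SD growth between square-root and proportional, power at the stated 12 days is about 65% to 51%. With all inputs at 12 months it is about 47%. A true 40% reduction would then be missed roughly one-third to one-half of the time. The range is illustrative and not a strict bound.

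It would be too strong to say that the Protocol's own numbers yield only about half power, since taken literally they yield 80%. The choice of a one-sided 5% level is a separate question; it is used here throughout because the Protocol uses it.

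**What to change.** Rewrite the power paragraph in Section 3.5:

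- Put the mean difference and the SD on the same time scale, preferably as a percentage of follow-up, to match Section 3.2.2.
- Use the unrounded difference (11.6 days from 29, or 11.4 from 28.5).
- Either justify an 18-month SD for this population or show a sensitivity range, for example 59 to 72 days, labelled as assumed. No single value in that range should be written in as established.
- Replace the unconditional 80% by the power that follows, and give the detectable difference at 199 per arm: about 15 days at SD 58.8 and about 18 days at SD 72.

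The cost is one paragraph and a less favourable stated power. No additional patients and no change to conduct are needed.
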